## 7.6 FURTHER ENDPOINTS

All further endpoints will take into account all data, regardless of whether the patient was on treatment or not, and without imputation of missing values (OC-AD).

### 7.6.1 Binary endpoints

For the following binary endpoints descriptive analyses will be complemented by an exploratory chi-square test to compare response between treatment groups.

- Increase in 6MWT  $\geq 30$  m from baseline at week 12
- Response in KCCQ domains at week 12, as defined in [Section 5.3](#). A forest plot of response at week 12 for each domain by treatment will be shown.
- Response in CHQ domains at week 12, as defined in [Section 5.3](#). A forest plot of response at week 12 for each domain by treatment will be shown.

Descriptive statistics are planned for all other binary endpoints:

- Occurrence of HHF and Cardiovascular (CV) death
- Occurrence of all-cause mortality
- Occurrence of CV death
- Occurrence of all-cause hospitalisation (first and recurrent)
- Occurrence of hospitalisation for HF (first and recurrent)
- Occurrence of all-cause emergency room visits (first and recurrent)
- Emergency room visit for HF (requires use of i.v. diuretics; first and recurrent)
- Occurrence of unscheduled outpatient visit (first and recurrent)
- Intensification of diuretic therapy (adding a new diuretic, increase of dose)
- Occurrence of MI (fatal or non-fatal)
- Occurrence of Stroke (fatal or non-fatal)
- Occurrence of TIA

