### 7.3.3 Further endpoint analyses

Endpoints describing responders such as increase in 6MWT  $\geq 30$  m or response in KCCQ or CHQ domains will be evaluated using a Chi-Square test.

Proportions of patients categorized by the shift in scores between baseline and week 6 in patient global impression of severity score will be evaluated using Cochran-Mantel-Haenszel test. Details on combining categories if the proportion of patients in one of the categories is small will be given in the TSAP.

Proportion of patients in every category of patient global impression of change at week 6 will be evaluated using Cochran-Mantel-Haenszel test. Details on combining categories if the proportion of patients in one of the categories is small will be given in the TSAP.

Proportion of patients in every category in clinician global impression of change at week 6 and week 12 will be evaluated using Cochran-Mantel-Haenszel test. Details on combining categories if the proportion of patients in one of the categories is small will be given in the TSAP.

Proportions of patients categorized by the shift in scores between baseline and week 6 (week 12) in clinician global impression of severity score will be evaluated using Cochran-Mantel-Haenszel test. Details on combining categories if the proportion of patients in one of the categories is small will be given in the TSAP.

Change from baseline continuous endpoints such as KCCQ domains or CHQ domains at week 6 and Week 12 will be evaluated using a MMRM analysis over time. The model will include treatment as fixed categorical effect and baseline of the respective endpoint as fixed continuous effect.

Change from baseline in Clinical Congestion Score at week 6 will be evaluated by the same MMRM used to evaluate Clinical Congestion Score at week 12 described for the secondary endpoint.

Change from baseline in NT-proBNP at week 6 will be evaluated by the same MMRM used to evaluate NT-proBNP at week 12 described for the secondary endpoint.

Proportions of patients categorized by the shift in scores between baseline and week 12 in NYHA class will be evaluated using Cochran-Mantel-Haenszel test. Details on combining categories if the proportion of patients in one of the categories is small will be given in the TSAP.

Change from baseline to week 12 in patient-rated assessment of dyspnea and fatigue by the Borg scale as part of the 6MWT will be presented descriptively.

Other further endpoints will be analysed descriptively.

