### **5.3 FURTHER ENDPOINTS**

Further endpoints are listed in CTP Section 2.2.2.

Response in KCCQ domains at week 12: Response will be defined as an improvement of at least 5 points.

Response in CHQ domains at week 12: Response will be defined as an improvement of at least 0.5 points. Scoring algorithm for all KCCQ domains and CHQ-SAS domains can be found in [Appendix 9.4](#).

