#### 7.5.1.4 Further exploratory analyses of the key secondary endpoints

A minimal clinically meaningful within-patient change in scores (i.e. responder threshold) will be estimated from the trial population (both treatment groups pooled) for KCCQ-TSS and CHQ-SAS dyspnea as described in [Appendix 9.3](#).

A responder analysis using a chi-square test will be evaluated in addition. The response threshold will be determined as defined in [Appendix 9.3](#).

An empirical cumulative distribution function of descriptive change from baseline to week 12 by treatment group on OC-AD on the randomised set will be shown.

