#### **Anchor**

The Patient Global Impression of Severity (PGI-S) of Dyspnea and PGI-S of Heart Failure Symptoms will each be used as the primary anchor for the CHQ-SAS Dyspnea scale and KCCQ-TSS, respectively. The Patient Global Impression of Change (PGI-C) of Dyspnea and PGI-C of Heart Failure Symptoms will be considered as secondary anchor scales for the CHQ-SAS Dyspnea scale and KCCQ-TSS, respectively.

A minimal clinically meaningful improvement for each PGI-S scale will be considered to be at least a one category improvement in change from baseline in PGI-S at week 12.

A minimal clinically meaningful improvement for each PGI-C scale will be considered to be at least “a little better” in PGI-C at week 12.

As an ancillary consideration, the distance walked in 6 minutes will be evaluated as a clinical indicator of patient improvement as well. Patients who improve at least 30 meters from baseline in distance walked in 6 minutes will be considered to be clinical responders [[R17-1227](#)] (5).

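### The exploratory responder comparisons use a valid but unadjusted chi-square test; adding the baseline value already collected would gain some power at no cost

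*SAP*

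**What the plan says.** Protocol 7.3.3 covers the 6MWT responder endpoint together with questionnaire response: "response in KCCQ or CHQ domains will be evaluated using a Chi-Square test". SAP 7.6.1 keeps this and labels it exploratory: "descriptive analyses will be complemented by an exploratory chi-square test to compare response between treatment groups". For KCCQ-TSS and CHQ-SAS dyspnea, SAP 7.5.1.4 adds: "A responder analysis using a chi-square test will be evaluated in addition". The threshold there is not fixed in advance; it is derived from the pooled trial data by the ROC method in SAP 9.3.

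The fixed thresholds are in SAP 5.3. For KCCQ domains: "Response will be defined as an improvement of at least 5 points". For CHQ domains: "Response will be defined as an improvement of at least 0.5 points". The 30 m criterion is in the endpoint definition (protocol 2.2.2), and SAP 9.3 uses the same cut-off: "Patients who improve at least 30 meters from baseline in distance walked in 6 minutes will be considered to be clinical responders".

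No baseline term or stratification is attached to any of these tests. Baseline is defined for every measure in SAP 6.7. It enters the MMRMs of 6MWT, KCCQ-TSS and CHQ dyspnea (SAP 7.4.2 and 7.5.1.2), the MMRMs of the other KCCQ and CHQ scores (SAP 7.6.3) and the ANCOVA models (SAP 7.6.3 and 7.8.2). It does not enter the Wilcoxon tests of the primary and key secondary endpoints (SAP 7.4.1 and 7.5.1.1).

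**The concern.** Response is a fixed amount of improvement, so the starting value can affect the chance of reaching it in two ways.

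- **Ceiling.** SAP 6.6.2 gives maxima of 100 for KCCQ-TSS and 7 for CHQ dyspnea. At the SAP 5.3 thresholds, a patient above 95 or above 6.5 at baseline cannot respond. 6MWT has no such ceiling: the 100 to 350 m limits apply at entry, not at week 12.
- **Regression to the mean.** Patients with a low baseline tend to improve more and those with a high baseline less, to an extent the documents do not quantify.

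If baseline predicts response, a test that ignores it has less power than one that uses it, and it cannot correct a chance difference between arms at baseline. Randomisation is unstratified (protocol 7.6). For the primary endpoint, SAP 7.4.2 plans a residual-rank analysis if mean baseline 6MWT differs by more than 15 m; the responder tests have no counterpart. These tests are the only planned inferential comparison of the proportion of patients reaching a meaningful improvement.

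**Working it through.** **1. The plan's own figures.** Protocol 7.7 assumes a 30 m difference, SD 72 m, two-sided 5% and 90% power. P(X<Y) = Φ(-30/(72·√2)) = 0.384. By the Noether formula, n per group = (1.960 + 1.282)² / (6·(0.3841 - 0.5)²) = 10.51/0.0806 = 130.4, so 131. The same formula gives 76 for 40 m and 50 for 50 m. All three match Table 7.7:1. Simulating the Wilcoxon test with worst-rank imputation at 150 per group gives 90.1%, 87.5% and 85.0% for 5%, 8% and 10% missing; Table 7.7:2 has 90%, 87% and 85%. No power is stated for any responder endpoint.

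**2. Chi-square power for 6MWT ≥30 m.** Take 30 m and SD 72 m from the protocol and assume a mean placebo change of 0.

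- Placebo response = 1 - Φ(30/72) = 33.8%; empagliflozin response = 50.0%; difference 16.2 points.
- Responder analyses are observed-case (SAP 7.6), so with 5% missing about 142 of 150 per arm count.
- Standard error: pooled √(0.419·0.581·2/142) = 0.0586; unpooled √((0.338·0.662 + 0.25)/142) = 0.0578.
- Power = Φ((0.1615 - 1.96·0.0586)/0.0578) = Φ(0.81) = 79%.

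**3. Adding baseline, 6MWT.** Simulation, 4,000 trials per row, 142 per arm, chi-square against logistic regression with a linear baseline term. The correlation of baseline with change (rho) is an assumption.

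| rho | Chi-square | Adjusted | Gain |
|---|---|---|---|
| 0 | 79.0% | 79.4% | 0.4 |
| -0.2 | 79.4% | 80.5% | 1.1 |
| -0.3 | 78.8% | 81.6% | 2.8 |
| -0.4 | 78.1% | 82.8% | 4.7 |
| -0.5 | 78.6% | 85.2% | 6.6 |

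A separate run at -0.5 gave 80% against 86%.

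**4. Adding baseline, questionnaires.** 3,000 trials per row, 142 per arm, scores clipped to the scale. From the protocol: KCCQ-TSS effect 5 and SD of change 15 (listed range 13 to 20); CHQ dyspnea effect 0.5 and SD 1.2 (range 1 to 1.4). Assumed: KCCQ baseline mean 65, SD 22; CHQ baseline mean 4.8, SD 1.2.

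| Measure | rho | Chi-square | Adjusted | Gain |
|---|---|---|---|---|
| KCCQ-TSS ≥5 | 0 | 53.8% | 55.0% | 1 |
| | -0.2 | 54% | 58% | 4 |
| | -0.34 | 54% | 59% | 5 |
| | -0.5 | 55% | 65% | 10 |
| | -0.6 | 56% | 69% | 13 |
| CHQ dyspnea ≥0.5 | 0 | 75.2% | 75.6% | 0.4 |
| | -0.2 | 73.7% | 76.0% | 2 |
| | -0.3 | 74% | 78% | 4 |
| | -0.5 | 75% | 83% | 8 |
| | -0.6 | 77% | 87% | 10 |

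Each power carries a Monte Carlo error of about 0.9 points, and repeat runs put the KCCQ gain at -0.5 as high as 11 and the CHQ gain at 0 at about 1. With a KCCQ baseline mean of 60 to 70, SD 21, a placebo change of +3 and rho -0.2 to -0.4, the gains were 2 to 8 points.

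The rho = 0 rows isolate the ceiling: it contributes about 1 point. The share of patients at the ceiling was 8.6% (KCCQ) and 7.8% (CHQ) under the main assumptions, and 5% to 12% for KCCQ baseline means of 60 to 70.

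**5. Which rho is plausible?** If baseline and week 12 variances are equal, rho = -SD(change)/(2·SD(baseline)). With the inputs above that is -15/44 = -0.34 for KCCQ and -1.2/2.4 = -0.5 for CHQ. The relation is not used for 6MWT, because the entry limits narrow the baseline spread but not the week 12 spread.

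**6. Type I error.** With no treatment effect (6MWT, rho -0.3 and -0.5), the chi-square test rejected in 5.2% and 4.1% of trials, and the adjusted test in 5.2% and 4.3%.

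**7. Chance imbalance.** Take the 15 m trigger of SAP 7.4.2 and an assumed 6MWT baseline SD of 55 m. The slope of change on baseline is rho·72/55, so rho -0.2 to -0.5 shifts the mean change by 15·0.262 = 3.9 m to 15·0.655 = 9.8 m. Near the threshold the response proportion moves by about φ(0.21)/72 = 0.0054 per metre, which gives 2 to 5 percentage points against an expected effect of 16.

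**The case against.** **The planned test is sound and nothing confirmatory rests on it.** This stands. The chi-square test holds its level. Both SAP sections present it as exploratory, the endpoints are outside the hierarchy, and no power is promised. A reader might infer that planned power is being given away; there is none to give away.

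**A reader might infer that these tests are the exception in a plan that otherwise always adjusts.** The documents do not support that. The primary and key secondary Wilcoxon tests are also unadjusted. The contrast is only with the MMRM and ANCOVA models.

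**A reader might infer that baseline strongly determines response.** The only mechanism the documents establish is the ceiling, which is worth about 1 point and does not exist for 6MWT. The rest of the gain comes from a correlation that the documents do not give. Gains of about 10 points or more on both questionnaires need rho near -0.6.

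**Baseline is already examined elsewhere.** The baseline-adjusted MMRMs, the baseline subgroups in SAP Table 6.4:1 and the residual-rank analysis all do so. This stands for the continuous scale, but none of them compares response proportions. Dichotomising also costs more than omitting baseline: at the 6MWT inputs above, a baseline-adjusted comparison of the continuous change would have 94% to 98% power for rho 0 to -0.5.

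**The KCCQ-TSS illustration is not the planned test.** This also stands. The 5-point rule in SAP 5.3 is for domains, while the TSS responder threshold in SAP 7.5.1.4 comes from the trial data. The gain for that analysis cannot be computed in advance.

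**Replacing the test departs from the protocol and makes the odds ratio conditional on baseline.** True; the fix allows for both.

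**Conclusion.** The point holds as a minor improvement. All tested responder endpoints ignore a baseline value that is available and that can only help. For rho between 0 and -0.5 the gain is about 0 to 6 or 7 power points for 6MWT, 1 to 8 for CHQ dyspnea and 1 to 11 for KCCQ-TSS at 5 points. No scenario showed a loss of power or a change in type I error. Adjustment also removes a shift of about 2 to 5 percentage points in the 6MWT responder difference if the arms differ by 15 m at baseline.

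These sizes rest on assumed correlations, baseline distributions and placebo changes, none of which the documents supply. What does not depend on them is that the chi-square is a valid test and that the primary and key secondary conclusions are unaffected.

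**What to change.** In SAP 7.5.1.4 and 7.6.1, add a logistic regression of response on treatment and the continuous baseline value of the same measure, on the same observed-case data. Report the odds ratio and a baseline-standardised risk difference with 95% CI, and keep the raw percentages by arm. The standardised risk difference keeps a marginal effect on the proportion scale.

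There are two ways to fit this with the protocol: keep the chi-square test and present the adjusted model beside it, or replace the test and list the change from protocol 7.3.3 in SAP 4.1. The first needs no departure from the protocol and achieves most of the benefit. If both are kept, the SAP should say in advance which result will be quoted.

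The cost is a few lines of SAP text and a standard procedure. No new data, visits or patients are needed.

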### 7.6.2 Ordinal endpoints

The following endpoints will be evaluated using the same models as defined for the corresponding secondary endpoints:

- Change from baseline in Patient Global Impression of Severity of Heart Failure Symptoms at week 6.
- Change from baseline in Patient Global Impression of Severity of Dyspnea at week 6.
- Patient Global Impression of Change in Heart Failure Symptoms at week 6.

- Patient Global Impression of Change in Dyspnea at week 6.
- Change from baseline in Clinician Global Impression of Severity of Chronic Heart Failure (CHF) at Week 6 and week 12
- Clinician Global Impression of Change in CHF Severity at Week 6 and week 12

Frequencies and proportions of patients categorised descriptively by the

- shift in NYHA class from baseline to week 6 and to week 12.

### **7.6.3 Continuous endpoints**

Further continuous endpoints are generally analysed in a mixed model with repeated measures (MMRM), including visit-by-treatment interaction and baseline-by-visit interaction. An unstructured covariance structure will be used to model the within-patient errors. The MMRM analyses will also be shown graphically.

Descriptive statistics will be calculated for the value at visit and change from baseline.

- Change from baseline in KCCQ overall summary score, CSS, and individual domains at Week 6 and week 12
- Change from baseline in CHQ individual domains at week 6 and week 12
- Change from baseline in SBP at Week 6 and week 12
- Change from baseline in DBP at Week 6 and week 12

The following endpoint is assessed as part of the main analysis or sensitivity analysis of the corresponding secondary endpoint:

- Change from baseline in KCCQ TSS at Week 6
- Change from baseline in CHQ-SAS dyspnea at Week 6
- Change from baseline in Clinical Congestion Score at week 6.
- Change from baseline in NT-proBNP at week 6.

Since bodyweight is only measured at baseline and week 12, an ANCOVA model will be presented including baseline weight as a covariate.

Descriptive statistics are planned for:

- Change from baseline to week 6 and week 12 in patient-rated assessment of dyspnea and fatigue by the Borg scale as part of the 6MWT

For the following parameters measured at the follow-up visit, additionally descriptive statistics at baseline, last value on treatment and follow-up will be presented for patients with valid measurements at all three timepoints. .

- SBP
- DBP

## **7.7 EXTENT OF EXPOSURE**

Descriptive statistics tables based on the TS with mean, SD, SE, quartiles, median and range of the number of days a patient was on treatment will be provided. These tables will also provide the sum-total of the time (in years) that all patients were on treatment.

Frequency tables of number and percentage of patients belonging to categorical ranges of exposure weeks will be provided as well. Following are the categories of exposure-ranges (in weeks):  $\geq 0$  weeks,  $\geq 4$  weeks,  $\geq 8$  weeks,  $\geq 11$  weeks.

## **7.8 SAFETY ANALYSIS**

The safety analysis will be based on the treated set (TS).

While tables will generally display results by randomised treatment, listings will reflect whether a measurement/AE occurred on or off treatment.

### **7.8.1 Adverse events**

Unless otherwise specified, the analyses of adverse events (AEs) will be descriptive in nature and will be based on the number of patients with AEs and not on the number of AEs.

AEs will be coded using version 22.0 of the Medical Dictionary for Regulatory Activities (MedDRA) coding dictionary.

Definitions of Boehringer Ingelheim customised MedDRA Queries (BIcMQs) for new MedDRA versions are maintained by the BI dictionary maintenance group.

For analysis multiple AE occurrence data in the data from the eCRF will be collapsed into an AE provided that all of the following applies:

- All AE attributes are identical (including Lowest Level Term (LLT), intensity, action taken, therapy required, seriousness, reason for seriousness, relationship, outcome, AE of special interest and also additional information of specific AEs or AESIs such anatomical location of UTI (upper UTI kidney versus Lower UTI bladder and below versus asymptomatic bacteriuria) or type of genital infection (fungal balanitis or vulvovaginitis versus other than fungal balanitis or vulvovaginitis)).
- The occurrences were time-overlapping or time-adjacent (time-adjacency of 2 occurrences is given if the second occurrence started on the same day or on the day after the end of the first occurrence).

For further details on summarisation of AE data, please refer to [\(2\)](#).

#### **7.8.1.1 Assignment of AEs to treatment**

The analysis of adverse events will be based on the concept of treatment-emergent adverse events. That means that all adverse events occurring between first drug intake till 7 days after last drug intake will be assigned to the randomised treatment. All adverse events occurring

before first drug intake will be assigned to ‘pre-treatment’ and all adverse events occurring after last drug intake + 7 days will be assigned to ‘follow-up’, except if otherwise specified.

In Section 15.3 general AE analysis tables will present only on-treatment AEs (applying the rule of 7 days for assignment as on-treatment) for the treatment groups.

Appendix 16.1.13.1 will include an analysis (overall summary table, frequency of AEs by system organ class (SOC) / preferred term (PT), frequency of serious adverse events (SAEs) by SOC/PT) where AEs and SAEs are assigned to the following phases: Screening, each treatment group, post-treatment for each treatment group.

For listings, AEs will be assigned to one of the treatment phases of Screening, Placebo, Empa 10, Post Placebo, Post Empa.

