### Information required

For each AE, the investigator should provide the information requested on the appropriate eCRF pages and the BI SAE form, if applicable. The investigator should determine the causal relationship to the trial medication.

The following should also be recorded as an (S)AE in the CRF and BI SAE form (if applicable):

- Worsening of the underlying disease or of other pre-existing conditions
- Changes in vital signs, ECG, physical examination and laboratory test results, if they are judged clinically relevant by the investigator.

If such abnormalities already pre-exist prior to trial inclusion they will be considered as baseline conditions and should be collected in the eCRF only. All (S)AEs, including those persisting after individual patient's end of trial must be followed up until they have resolved, have been assessed as "chronic" or "stable", or no further information can be obtained.

For some types of AEs additional information will be collected in the eCRF due to the nature of the event and mechanisms of action of the trial medication. These listed AEs are distinct from AESI. The list of types of AEs for which additional information will be collected may change during the trial based on potential new knowledge about the safety profile of empagliflozin:

- Hypoglycaemic event
- Genital infection
- Acute pyelonephritis
- Sepsis
- Urinary tract infection
- Bone fracture
- Hypotension

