#### **7.3.4 Safety analyses**

Adverse events will be coded using the Medical Dictionary for Drug Regulatory Activities (MedDRA). Standard BI summary tables and listings will be produced. All adverse events with an onset between start of treatment and end of the residual effect period (REP), a period of 7 days after the last dose of trial medication, will be assigned to the on-treatment period for evaluation.

All treated patients will be included in the safety analysis. In general, safety analyses will be descriptive in nature and will be based on BI standards. No hypothesis testing is planned.

Statistical analysis and reporting of adverse events will concentrate on treatment-emergent adverse events, i.e. all adverse events occurring between start of treatment and end of the residual effect period. Adverse events that start before first drug intake and deteriorate under treatment will also be considered as 'treatment-emergent'.

Frequency, severity, and causal relationship of adverse events will be tabulated by system organ class and preferred term after coding according to the current version of the Medical Dictionary for Drug Regulatory Activities (MedDRA) at the database lock.

Laboratory data will be analysed both quantitatively as well as qualitatively. The latter will be done via comparison of laboratory data to their reference ranges. Values outside the reference range as well as values defined as clinically relevant will be summarised. Treatment groups will be compared descriptively with regard to distribution parameters as well as with regard to frequency and percentage of patients with abnormal values or clinically relevant abnormal values.

Vital signs, physical examinations, or other safety-relevant data observed at screening, baseline, during the course of the trial and at the end-of-trial evaluation will be assessed with regard to possible changes compared to findings before start of treatment.

Reasons for discontinuation and use of post-baseline concomitant medications will be tabulated.

The details of the analysis will be specified in the TSAP.

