## **4. CHANGES IN THE PLANNED ANALYSIS OF THE STUDY**

### **4.1 CHANGES NEWLY INTRODUCED FROM THE CLINICAL TRIAL PROTOCOL**

Analyses of the following endpoints have been added:

- Systolic blood pressure
- Diastolic blood pressure
- Body weight

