7.8.1.7 Adverse event incidence rates

For AE tables showing patients with events, in addition to the frequency tabulations, time-adjusted adverse event analyses will be performed for all AEs, investigator defined drug-related AEs, AEs leading to discontinuation, serious AEs, and adverse events of special interest by SOC and PT or High-Level Term (HLT) and PT, respectively.

The time at risk in patient years for the on-treatment phase is derived as follows:

Patients with AE:

time at risk (AE) in days = date of start of AE with specified PT/SOC/HLT – study treatment start date + 1

Patients without AE:

time at risk (AE) in days = end date of time at risk – study treatment start date + 1, where end date of time at risk is the minimum of date of last study drug intake + x days and date of death, if applicable.

The standard approach will be x=7 days, but for certain AESIs in addition other approaches will be used.

Total AE-specific time at risk per treatment group is then derived as:

Time at risk (AE) [years] = Sum of time at risk [days] over all patients in a treatment group / 365.25

For 'each row of a table' (e.g. displaying an SOC), time at risk is calculated using start of first AE summarised in this row; e.g. for patient with AE in a specified SOC, time at risk = date of start of AE with specified PT in this SOC – start of study treatment + 1.

The AE incidence rate per 100 patient years will then be calculated as follows:

Incidence rate per 100 patient years (pt-yrs) =  $100 * \text{number of patients with AE} / \text{time at risk (AE) [years]}$ .

In a similar way the time at risk and incidence rate for the post-treatment period is derived. Hereby the start date is the start date of the post-treatment phase instead of the study treatment start date.

For some specific outputs showing number of episodes, event rates will be defined as number of episodes divided by time at risk. Time at risk will be end date of time at risk – study treatment start date + 1, where end date of time at risk is the minimum of date of last study drug intake + x days and date of death, if applicable.

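### SAP 7.8.1.1 leaves out the protocol's rule that adverse events starting before first dose and worsening on treatment are treatment-emergent, and does not declare the change

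*SAP*

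**What the plan says.** Protocol 7.3.4 sets the on-treatment window from start of treatment to the end of the residual effect period, "a period of 7 days after the last dose of trial medication". It then adds a second route into the treatment-emergent category: "Adverse events that start before first drug intake and deteriorate under treatment will also be considered as" treatment-emergent.

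SAP 7.8.1.1 says that the AE analysis rests on the treatment-emergent concept and explains it with the window alone: "all adverse events occurring between first drug intake till 7 days after last drug intake will be assigned to the randomised treatment". Whatever occurs ahead of the first dose goes to a pre-treatment category instead, subject to exceptions specified elsewhere. The same section restricts the main output: "In Section 15.3 general AE analysis tables will present only on-treatment AEs". Screening-phase events go to Appendix 16.1.13.1 and the listings.

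SAP 7.8.1.7 computes incidence rates with "time at risk (AE) in days = date of start of AE with specified PT/SOC/HLT", minus the treatment start date, plus one.

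SAP 4.1, the list of departures from the protocol, opens with "Analyses of the following endpoints have been added" and names only systolic pressure, diastolic pressure and body weight.

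**The concern.** The SAP presents itself in Section 3 as a more detailed elaboration of protocol Section 7. Here it applies a narrower definition than the protocol without saying so. The 7-day window agrees in both documents. The part missing from the SAP is the one that catches worsening on drug of something already present at screening.

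Such records can exist. AEs are collected from informed consent (protocol 5.2.7.2) and screening lasts up to 3 weeks (protocol 3.1). Events must be followed until they resolve, are judged chronic or stable, or no more can be learned, so an event opened in screening can still be open at first dose.

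If such an event stays on one record with its pre-dose start and then worsens on treatment, the protocol places it in the treatment-group tables and the SAP places it outside them. The tables and rates would then follow a definition other than the one the protocol states, and a reader of the report would not be told.

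**Working it through.** The plan gives no figure for this point, so there is none to reproduce. The check compares the texts and applies the SAP's own time-at-risk formula.

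**1. The two definitions**

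| | Protocol 7.3.4 | SAP 7.8.1.1 |
|---|---|---|
| Event starts between first intake and last intake + 7 days | Treatment-emergent | Randomised treatment |
| Event starts before first intake, does not worsen | Not treatment-emergent | Pre-treatment |
| Event starts before first intake, worsens on treatment | Treatment-emergent | Pre-treatment |

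Only the third row differs.

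**2. Does the SAP's word *occurring* cover worsening events?** Protocol 7.3.4 uses both *onset* and *occurring* for the same window, and then needs a separate sentence to bring in deteriorating events. In the protocol's own usage, *occurring* in the window does not include them.

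**3. Is an exception specified elsewhere?** The exceptions in SAP 7.8.1 to 7.8.1.7 concern the end of the window. Examples are the 30 days after treatment stop for adjudicated hepatic events (7.8.1.5) and the other follow-up lengths for certain AESIs (7.8.1.7). None concerns a pre-dose event that worsens. The visible entries of the history table in SAP Section 10 do not mention one either.

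**4. The time-at-risk formula.** Let T be the treatment start date and let the event start k days before it.

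- Time at risk = (T − k) − T + 1 = 1 − k days
- k = 1: 0 days
- k = 21 (full 3-week screening): −20 days

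The formula gives no usable value for the events in the third row. The SAP's rate calculation therefore assumes an on-treatment start date.

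**5. What one such patient does to a table row.** Take a patient who completes treatment on planned day 85, with no other event in that row.

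- SAP as written: counted as a patient without the event. Time at risk = (T + 84 + 7) − T + 1 = 92 days, with 0 events.
- Protocol rule, worsening on planned day 43 and dated there: (T + 42) − T + 1 = 43 days, with 1 event.
- Protocol rule with first intake used as the start: T − T + 1 = 1 day, with 1 event.

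The last line shows why the choice of start date has to be written down. Dating every such event to first intake would cut the time at risk to one day.

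**6. When the event is not lost.** Protocol 5.2.7.2 asks sites to record as an AE "Worsening of the underlying disease or of other pre-existing conditions". SAP 7.8.1 collapses occurrences into one AE only if every attribute matches, including intensity and seriousness. A worsening entered as a new occurrence with a different intensity stays separate, has an on-treatment start date, and enters the Section 15.3 tables. The loss is confined to worsenings held on a single record with a pre-dose start. The documents do not say how the eCRF handles worsening of an AE already opened in screening.

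**The case against.** The strongest reply is that the SAP abbreviates the protocol and does not override it. SAP Section 3 says the plan builds on protocol Section 7, SAP 7.8.1.1 adopts the treatment-emergent concept by name, and some AE detail is referred to company guidance that is not in these documents. A programmer who knows the protocol might apply its full definition. That is possible, but the SAP does more than stay silent: it states where pre-dose events go and gives a rate formula that cannot take the others.

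A second reply carries more weight. A reader might infer that worsening events drop out as a class, or that the plan could conceal harm in the empagliflozin arm. The documents do not support either reading:

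- **Recording.** A worsening entered as a new occurrence is counted, as shown above.
- **Urinary infection.** An acute episode at screening is documented as history or a baseline condition (protocol 5.2.4.4), so a later worsening is recordable as an AE.
- **Heart failure.** Worsening of the underlying disease is recordable. Decompensation needing intravenous therapy during screening is exclusionary (exclusion criterion 2), and stability at randomisation is required (inclusion criterion 9).
- **Hypotension.** Symptomatic hypotension or low systolic pressure at Visit 1 or 2 is exclusionary (exclusion criterion 6).
- **Renal and hepatic worsening.** Creatinine, eGFR and liver enzyme tables rest on laboratory values (SAP 7.8.1.3 and 7.8.2), not on AE start dates.
- **Reporting.** Screening-phase events still appear in Appendix 16.1.13.1 and in the listings.

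These points limit the likely size. They do not bring the two definitions into agreement.

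**Conclusion.** The discrepancy is real and undeclared: the SAP's assignment rule is narrower than the protocol's definition of treatment-emergent. It should be corrected, as a point of descriptive safety reporting.

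Its size cannot be derived. The documents give neither a rate of screening AEs, nor a rate of worsening, nor the eCRF practice on which the loss depends. A count of patients affected, or a share of events lost for a given term, would be guesswork, and the number may be small. Nor do the documents show that any loss would fall more on one arm.

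The conclusion rests on one assumption: that the SAP is programmed as written. Laboratory-based tables and the primary and key secondary analyses are not affected.

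**What to change.** 1. In SAP 7.8.1.1, add the protocol's second criterion and define deterioration operationally. One workable definition: an event with a pre-dose start is treatment-emergent under the randomised treatment if it increases in intensity or becomes serious between first intake and last intake + 7 days. The protocol does not define the word, so this definition should be identified as the SAP's own.
2. In SAP 7.8.1.7, state that the date of worsening is the event start for time at risk, and give a rule for when that date is not recorded. If first intake is the fallback, say so and note that it yields one day at risk.
3. Confirm how the eCRF records worsening of an AE opened in screening, and check that one worsening cannot be counted both as a new occurrence and through the new rule.

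If the narrower definition is intended, the alternative is to declare and justify it in SAP 4.1.

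The cost is a short text change, one extra derivation and slightly higher AE counts. No new data are needed where the date of worsening is captured.
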